5.1 Study Design and Methods

5.2 Overview

This will be randomized, placebo controlled, double blinded study

We plan to enroll fifty subjects with homozygous sickle cell disease (HbSS), sickle-thalassemia (Hb S-ß thalassemia), HbSC, HbSD, or HbSO^{Arab}, in order to have 40 subjects complete at least 8 weeks of treatment, after an expected 20% dropout.

Subjects will receive 2% topical sodium nitrite cream twice a week for 10 weeks or placebo with vehicle only.

Subjects will have 0.1 cm of 2% sodium nitrite cream or placebo cream applied per 1 cm² of the total ulcerated area. If a subject has more than one ulcer, all of them will be treated with either "study cream" or placebo. Areas will be rounded to the nearest 1 cm². If a subject has more than one ulcer and the total sum of all of them is above 100 cm², then one of the ulcers can be enrolled

PI: [name]

^{*} If a patient does not qualify because he/she has an infection at the time of enrollment or at run-in, he/she can initiate the protocol two weeks after the infection has been cleared.

in the study, as long as it does not exceed the 100 cm² size. The other wounds will continue standard of care only. The total amount of sodium nitrite administered to each subject will vary depending upon the size of the ulcer but the treated total surface area will not exceed 100 cm² (i.e., subjects will receive a maximum of 10 cm of sodium nitrite cream).

Administration of study cream or placebo will be double blinded. The pharmacist will not be blinded, so he/she will be aware of who is receiving the investigational drug for safety purposes.

Randomization:

Randomization will be stratified by use of hydroxyurea to minimize its potential confounding effect on the study outcomes; we expect that 50% of participants use hydroxyurea. In addition, within each stratum (use or non-use), random treatment assignment will be balanced, i.e., 1:1 allocation, within blocks. This type of stratified block-randomized allocations will be generated by the study statistician applying a computer algorithm. The randomized allocation will occur once a subject is determined to be eligible for participation after the screening visit and the run in phase, but prior to the first cream application.

Un-blinding Procedures:

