PI: [name] Version 5 in order to assess cutaneous vascularization (i.e., angiogenesis), inflammation (tissue II-6, TGF- \Box , etc.), and markers of neurogenic inflammation³⁶.

At the end of 10 weeks of treatment, subjects that still have an open ulcer will be offered continuation of care at Montefiore or University of Pittsburg or referred back to the community.

Subjects will be followed off treatment but on study with monthly visits for an additional six months to evaluate the long term effect of topical sodium nitrite on the host and the ulcer (how many ulcers re-open or close). These visits will consist of measurement of all wounds by light photography and a detailed history of intervening ulcer treatments. If patients cannot return to the hospital or have moved away, we will call them and obtain the information on the phone and ask for a photograph. The photo can be obtained by the patient him or herself. Thereafter, they will be followed up with phone calls once a year for a total of 2 years, to establish whether this therapy is changing the natural history of ulcers in this population.

Rationale for the selection of subjects' number and endpoints

Sample size: We plan to randomize a total of 50 subjects to sample size of 20 completers per arm (40 subjects total) after an anticipated 20% dropout rate is taken into account. This sample size is determined based on feasibility of recruitment within the budget constraint and time frame of the study; we anticipate enrolling 1~2 eligible subjects per month. Although the focus of analysis will be more on estimation of treatment effect sizes and their 95% confidence intervals, the anticipated sample size is adequate to detect 88% vs. 48% response rate, as defined by >25% reduction of ulcer size from baseline, between treatment and control groups, with >80% at a two-sided significance level of 0.05 (see table 1). We note that in the Phase 1 study we observed an 88% response rate. Therefore, our study will be adequately powered if response rate in the placebo group is smaller than 48%.

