Week 2-10/ Visits 4-22: The subjects will be seen twice a week for cream application, wound care and monitoring of side effects. The wound will be measured once a week manually by the wound care nurse and measured by photography after 10±2 applications. Blood pressure and vital signs will be measured upon arrival to outpatient unit and 30 minutes±10 minutes after the application of the study cream, unless clinically indicated. If the blood pressure is stable after cream application for all visit 4, 5, 6, post cream application blood pressure monitoring wound not be needed for future study visits. The wound will be cleaned and study cream will be applied.

Routine bloods will be drawn as clinically indicated. A research methemoglobin level will be obtained every other week.

A repeat pregnancy test will be performed at week 4 in women of reproductive age. Pain assessment: a VAS scale will be obtained with each application of the study cream. If there is more than one ulcer, individual VAS scale per ulcer will be obtained.

After the first three subjects have completed the first application of the study drug, if there are no significant side effects, especially significant changes in BP, patients will be offered the option of applying the second weekly dose of the cream at home, by themselves or by a home health nurse. We will dispense the exact amount of cream to be applied eachweek. This will reduce the number of visits to the wound care / hospital location to once a week.

End of study: Subjects will return the week after the last application to have the study cream removed and for end of study procedures. Blood pressure and vital signs will be measured with a pulse oximeter. The surface area of all ulcerated surfaces will be measured and photographed with defined lighting, distance, exposure, and camera. The wound doctor or nurse will remove the "study cream" and obtain a repeat microbiome sample. A VAS scale will be obtained to assess pain. If there is more than one ulcer, individual VAS scales will be obtained per ulcer. ASCQ-ME, PROMIS, BDI, and BPI surveys will be distributed to the patient. Study labs will be obtained (see Appendix 1). Patients who discontinue the study will still receive end of study procedures.

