7.2 Stopping Rules

The study medication will be stopped if the subject experiences healing of the ulcer.

Subjects will be removed from therapy should one or more of the following occur:

- If any methemoglobin reading is >7.5%, the research study cream will be discontinued.
- Investigator or patient considers discontinuation of the study to be in the patient's best interest.
- Clinically significant hypotension (decrease in the systolic BP >20mmHg from the baseline systolic BP and of 10mmHg from the baseline diastolic BP application, and symptomatic dizziness, tachycardia, or hypoxia as per the judgment of the PI).
 - A dose will be skipped if the subject has a systolic blood pressure of ≤80mmHg and/or a diastolic blood pressure of ≤50mmHg, once the blood pressure has been checked with a repeat blood pressure check. If three doses are skipped in a row for this reason, the subject will be removed from therapy.
- Sustained pulse oxygen saturation below 85% for >15 minutes while on supplemental oxygen (up to 4L by NC).

- Increased ulcer pain requiring increased opioid use by 50%.
- Development of osteomyelitis or other systemic infection while on therapy.
- Lack of compliance, as measured by missing more than two sequential cream applications and/or at the PI's discretion.

Rules for Stopping the Study:

- Occurrence of severe toxicities:
 - Three subjects requiring sodium nitrite cream discontinuation
 - Death while on protocol, if it is attributable to the sodium nitrite cream

8. **Analysis of the Study**

We will first review and summarize data using descriptive summaries and graphical analyses to ensure recorded values are within appropriate ranges, in order to check for outliers and abnormal values. We will explore the success of randomization by comparing groups on potential confounding variables, and will include variables that are not equally distributed between groups in multivariable models. For primary analyses, we will adhere to the intent-totreat analysis principle that assigns groups as randomized as opposed to actually treated. For sensitivity analyses, we will conduct as-treated analysis and use incomplete data as well after imputation of missing data due to early dropouts; imputation methods such as last-observationcarried-forward or MCMC will be conducted and results from thereof will be compared.

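### The healing and pain responder tests ignore the hydroxyurea strata used in randomisation, and adjustment covariates are to be chosen by observed imbalance

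*Combined protocol and SAP*

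**What the plan says.** Section 5.2 gives the reason for the design: "Randomization will be stratified by use of hydroxyurea to minimize its potential confounding effect on the study outcomes". Allocation is 1:1 in blocks within each stratum, and "we expect that 50% of participants use hydroxyurea".

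Sections 8.1.2 and 8.1.3 test healing response and pain response with a chi-square test. Neither names a stratum term. Logistic regression is available if confounders are judged to need it. Both sections add mixed models for the weekly measurements, again without naming covariates.

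The general rule for covariates is in section 8 (Analysis of the Study). Groups are compared at baseline, and the analysts "will include variables that are not equally distributed between groups in multivariable models". Section 8.2.1 gives hydroxyurea its own secondary analyses, including an interaction with treatment.

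Section 5.2 states the aim of the efficacy analysis: "the focus of analysis will be more on estimation of treatment effect sizes and their 95% confidence intervals". Power is given for a "sample size of 20 completers per arm (40 subjects total) after an anticipated 20% dropout rate is taken into account".

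On the analysis set, section 8 says: "For primary analyses, we will adhere to the intent-totreat analysis principle that assigns groups as randomized as opposed to actually treated". Section 5.3 adds: "Patients who discontinue the study will still receive end of study procedures". Imputation appears in section 8 only under sensitivity analyses.

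**The concern.** A factor important enough to stratify on should be in the analysis. If it predicts response, the pooled chi-square test counts the variation between strata as noise. The test is then conservative, and its true error rate depends on an unknown hydroxyurea effect.

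The optional logistic model does not close the gap. Its covariates come from the imbalance rule, and stratified blocks make hydroxyurea the variable least likely to look imbalanced. The rule also has no variable list and no threshold, so the adjusted model can be settled only after the data are seen. In a trial meant to supply effect sizes and confidence intervals, the lead estimate should come from a model fixed in advance.

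**Working it through.** **Inputs.** From section 5.2: response 88% vs 48%, two-sided 5%, 20 completers per arm, 50 randomised, 20% dropout, 50% on hydroxyurea. Assumed: the odds ratio (OR) of hydroxyurea for response, the same in both arms, at 1, 2, 3.5 and 9. No pain response rate is given, so the figures are for healing only.

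**The plan's own figure.** 40 / (1 - 0.2) = 50. Power at 20 per arm for 88% vs 48% is 79.7% by the pooled normal formula and 82.1% by exact enumeration of the uncorrected chi-square test. The stated figure of over 80% reproduces.

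**Why the chi-square test becomes conservative.** Take OR 9 with 48% response in both arms. Stratum rates that average 48% with an OR of 9 are about 73% and 23%. The mean within-stratum variance is (0.7295 x 0.2705 + 0.2305 x 0.7695) / 2 = 0.187. The pooled test uses 0.48 x 0.52 = 0.250. The denominator is too large, so rejections are too few.

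**Exact enumeration, 10 per arm in each stratum.** Type I error is at 48% in both arms. Power and coverage are at 88% vs 48%. The intervals are Wald intervals for the response difference.

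| Assumed OR | Type I error, chi-square / CMH | Power, chi-square / CMH | Coverage, unstratified / stratified |
|---|---|---|---|
| 1 | 4.3% / 4.2% | 82.1% / 80.6% | 93.5% / 92.7% |
| 2 | 4.0% / 4.3% | 82.3% / 81.6% | 93.8% / 92.7% |
| 3.5 | 3.3% / 4.6% | 82.9% / 83.6% | 94.5% / 92.7% |
| 9 | 1.9% / 4.9% | 84.4% / 87.8% | 96.2% / 92.8% |

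At OR 3 power is 82.7% vs 83.0%, which is the break-even point.

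The unstratified 95% interval is 2 x 1.96 x sqrt(0.88 x 0.12/20 + 0.48 x 0.52/20) = 52.2 points wide. The stratified width is 52.2, 51.6, 50.2 and 46.8 points at the four ORs. The coverage column shows that the stratified Wald interval is too narrow for its nominal level. One cause is sparse cells. At OR 1 the chance that at least one treated stratum of 10 has no non-responder is 1 - (1 - 0.88^10)^2 = 48%, and at OR 9 it is 77%.

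**Would the imbalance rule pick hydroxyurea?** With 25 randomised per arm, a split of 13 vs 12 gives chi-square = (1/25)^2 / (0.5 x 0.5 x 2/25) = 0.08, p = 0.78. After a random loss of 5 per arm, hydroxyurea is flagged in 0% of trials at p<0.05 and 0.4% at p<0.20. An unstratified covariate with 50% prevalence is flagged in 4.3% and 19%. The cut-offs are assumed, since section 8 gives none.

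**What the open rule can do.** With 5 independent covariates (assumed), at least one reaches p<0.10 in 1 - 0.9^5 = 41% of correctly randomised trials. In a null simulation at 20 per arm (8,000 trials per setting, assumed OR 1.5 or 2 per SD), one fixed threshold gives a type I error of 3.4 to 4.5%, against 4.2 to 4.6% unadjusted. Reporting the smallest p-value over the unadjusted test and three thresholds gives 5.6 to 6.0%.

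**The case against.** The strongest reply is that stratified randomisation already controls confounding, that sections 8.1.2 and 8.1.3 permit adjustment, and that section 8.2.1 models hydroxyurea directly. The declared primary endpoint is tolerability and adverse events, and efficacy is mainly for estimation. No document says that hydroxyurea predicts healing. Below an OR of about 3 CMH loses a little power, and a stratified Wald interval covers less well than the planned one up to OR 3.5. The excess error from covariate selection needs an analyst to report the best of several models, which nobody plans.

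Much of this stands. It makes the gain modest and conditional, and it rules out the Wald interval. It does not rescue the imbalance rule, which would leave hydroxyurea out in practice. Section 8.2.1 asks about the hydroxyurea effect and its interaction with treatment. It does not give a treatment comparison adjusted for the stratum.

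Three stronger readings are tempting, and the documents do not support them:

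- **The unstratified test raises false positives.** The error rate falls as hydroxyurea becomes more prognostic.
- **The power statement is wrong because intent-to-treat covers 25 per arm.** The statement is explicitly for 20 completers per arm and is right for them. Leaving out 5 of 25 per arm gives the same 82.1%.
- **Dropouts are necessarily excluded.** Intent-to-treat and the end-of-study procedures for discontinuers point the other way.

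**Conclusion.** The point holds as a mismatch between design and analysis, together with a data-dependent covariate rule. It is worth correcting, but the planned tests are not invalid. The planned test's type I error is 4.3% falling to 1.9% over assumed ORs of 1 to 9, against 4.2 to 4.9% for CMH. The change in power runs from a loss of 1.5 points to a gain of 3.4 (87.8 - 84.4). All of this assumes 20 per arm split evenly by hydroxyurea and the same OR in both arms.

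A minor gap remains: no rule classifies a randomised subject who has no final value. A reader might think that equal loss in both arms makes leaving such subjects out harmless. That is true only when the response rates are equal. Suppose 20% are lost in each arm and non-responders are lost 3 times as often. The share of responders lost is q = 0.2 / (p + 3(1 - p)), and the observed rate is p(1 - q)/0.8. This gives 92.3% for p = 0.88 and 54.1% for p = 0.48. The difference is 38.1 points instead of 40, a bias of -1.9. The loss pattern is an assumption.

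**What to change.** - Make both responder tests CMH tests stratified by hydroxyurea as randomised.
- Report the stratified response difference with a small-sample interval, for example a stratified score (Miettinen-Nurminen) or Newcombe type. Check its coverage at about 10 per arm per stratum before fixing the choice.
- Put hydroxyurea and the baseline value in the mixed models as fixed covariates.
- Delete covariate selection by observed imbalance and keep the baseline comparison descriptive. A logistic model with several covariates is not a good substitute: only 20 x (0.12 + 0.52) = 12.8 non-responders are expected among 40.
- State that the responder analyses use all randomised subjects, including the end-of-study values of discontinuers, and name the rule when no final value exists.

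The cost is plan wording, with no new data or visits. CMH loses 1.5 points of power at OR 1 and 0.7 at OR 2 with 20 per arm. The power paragraph in section 5.2 needs no correction for the planned chi-square test. If CMH replaces it, 80.6% at OR 1 still exceeds 80%.

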8.1 Primary Endpoints and Analysis

The primary endpoint of this phase II study will be the assessment of tolerability and occurrence of adverse effects of topical sodium nitrite compared to placebo.

- 8.1.1 Frequency of each adverse event will also be tabulated. To compare the safety of prolonged (10 weeks) treatments between the experimental/treatment and usual care/placebo groups, we will apply a non-parametric Mann-Whitney test on the number of adverse events.
- 8.1.2 Effect sizes of the treatment on the ulcer size reduction will be determined by differences in response rates or odds-ratios, and the 95% Cl's will accordingly be To test if topical sodium nitrite accelerates wound healing, as defined by >25% improvement over placebo arm, we will apply a Chi-square test. Logistic regression models will be applied if inclusion of confounding variables deems necessary. We will also test if declines of weeklymeasured absolute ulcer size on a continuous scale over the study period will be different between the two groups by applying mixed effects linear models for analysis of repeatedmeasure outcomes.
- 8.1.3 Effect sizes of the treatment on the pain reduction will be determined by differences in response rates or odds-ratios, and the 95% CI's will accordingly be estimated. To test if topical sodium nitrite decreases pain at the wound site >20% over placebo, we will apply a Chisquare test. Logistic regression models will be applied if inclusion of confounding variables deems necessary. We will also test if declines of weekly-measured absolute pain VAS scores on a continuous scale over the study period will be different between the two groups by applying mixed effects linear models for analysis of repeated-measure outcomes.

25

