3.0 Specific Aims

Hypotheses:

- •Topical sodium nitrite cream, at 2% concentration, is safe and well tolerated when applied for an extended period of time (10 weeks) in patients with sickle cell disease and leg ulcers.
- •Topical sodium nitrite accelerates healing of skin ulcers and decreases ulcer relatedpain compared to placebo in patients with sickle cell disease and leg ulcers.

Specific Aims:

- To determine the safety and tolerability of prolonged (10 weeks), twice a week application of topical sodium nitrite in patients with sickle cell disease and leg ulcers
- To determine if topical sodium nitrite accelerates wound healing as defined by >25% improvement over placebo arm
- •To determine if topical sodium nitrite decreases pain at the wound site >20% over placebo

Secondary Objectives:

- To evaluate the effect of hydroxyurea on leg ulcer's healing in combination with topical sodium nitrite or placebo
- To assess changes in ulcer microbiome after application of sodium nitriteor placebo and how they may relate to rate of healing
- •To evaluate the dermal composition and microvascular structure in the ulcer's biopsy of subjects enrolled on this study.

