5.4 Dose Adjustment

Sodium nitrite dose will be modified according to this scheme:

- a) If a subject's ulcer surface decreases by more than 50% of the original area, as measured after 10 applications, a 50% reduction in the dose of sodium nitrite willtake effect for the remaining applications.
- b) If a subject's ulcer(s) increase by 50% of the original area, as measured after10 applications, a 50% increase in the dose of sodium nitrite will take effect for the remaining applications.

Dose-limiting toxicities are defined as:

- Severe stinging pain or burning sensation, requiring a 50% increase in opioiduse.
- •Peripheral edema causing significant discomfort by patient subjective report.
- Clinically significant hypotension or symptomatic dizziness, tachycardia, or hypoxia as per the judgment of the PI
- •Methemoglobinemia >7%

In the event that a subject experiences dose limiting toxicity, he/she will discontinue participation in the protocol.

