PI: [name] Version 5 62/077,622, filed on November 10, 2014, entitled "TOPICAL SODIUM NITRITE FORMULATION," and PCT Patent Application No. PCT/US2015/060015, filed on November 10, 2015, entitled "TOPICAL SODIUM NITRITE FORMULATION," has six inventors: [name], [name], [name], [name], [name], and [name], who were all NIH employees at the time of invention.

- Or. [name] is presently employed on the faculty of the University of Pittsburgh.
- oDr. [name] is presently employed on the faculty of the Albert Einstein College of Medicine.

12 Adverse Events Reporting

The Principal Investigator (or a physician member of the research team) and the study coordinator will assess each participant for any new or continuing adverse events. An adverse event is defined as any untoward medical occurrence in a subject of a clinical investigation that involves the administration of a pharmaceutical product. The event need not to have a causal relationship with the treatment. This includes any events that are not seen at baseline or, if present at baseline, have worsened in severity. These adverse events will only be collected during study treatment time. The severity and drug relationship will be determined, and any management required will be recorded. The investigator will review the clinical laboratory test results in a timely fashion. Only those results qualifying as adverse events, as defined above, will be recorded as an adverse event.

Table 2. Expected Adverse Events Possibly Related to Study Drug						
Severe stinging and burning sensation, requiring an increase in narcotic use.						
Peripheral vasodilation with hypotension (BP below 85/50, or symptomatic						
dizziness, tachycardia, or hypoxia as per the judgment of the PI)						
Methemoglobinemia >7.5%						

Acute chest syndrome Angioedema Angioedema Aplastic crisis Aplastic crisis/anemia Aplastic crisis/anemia Appendicitis Bone Infarction Cardiomegaly Cerebrovascular accident Cholecystitis, hepatic sequestration Cranial nerve palsy Decreased kidney function Decreased lung function Pever Renal Insufficiency/albuminuria Headache Hematuria Hematuria Reticulocytosis (10%-20%) Hemiplegia Hemolysis Hepatosplenomegaly Hyperplastic bone marrow Hyposthenuria Increase Jaundice Metabolic acidosis	Table 3. Expected Adverse Events Re	elated to Sickle Cell Disease

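### Tolerability is half of the primary endpoint, but the only between-arm safety test compares raw adverse-event counts, which respond weakly to treatment-ending toxicity and can move the wrong way

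*Combined protocol and SAP*

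**What the plan says.** The first specific aim in Section 3.0 is "To determine the safety and tolerability of prolonged (10 weeks), twice a week application of topical sodium nitrite". Section 8.1 defines the primary endpoint as "the assessment of tolerability and occurrence of adverse effects of topical sodium nitrite compared to placebo". Both name tolerability, and the second sets it against placebo.

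The analysis of that endpoint, in Section 8.1.1, has two parts: "Frequency of each adverse event will also be tabulated", and "we will apply a non-parametric Mann-Whitney test on the number of adverse events". Ulcer size and pain (8.1.2 and 8.1.3) receive more: responder proportions or odds ratios with 95% CIs, and mixed models.

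Events that would mark the cream as not tolerated are described elsewhere. Section 5.4 lists dose-limiting toxicities and adds: "In the event that a subject experiences dose limiting toxicity, he/she will discontinue participation in the protocol". Section 7.2 lists reasons for removal from therapy and a study-level rule triggered by three subjects having to discontinue sodium nitrite cream. Section 12 (Adverse Events Reporting) says "The severity and drug relationship will be determined, and any management required will be recorded", and also "These adverse events will only be collected during study treatment time". Section 8 does not use dose-limiting toxicity, removal, severity or relatedness in any comparison between arms.

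**The concern.** Tolerability has no operational definition and no analysis of its own, so the test on event counts has to stand in for it. Two features make it a poor substitute.

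First, a count carries no weight for consequence. Section 12 counts any untoward event, causal or not, in a population with a long list of expected sickle cell events. A subject with one treatment-ending toxicity ranks below a subject with two trivial events.

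Second, the collection window closes when treatment stops. A subject removed for toxicity contributes that event and then nothing more. Section 7.2 also stops the cream on healing, so faster healing would shorten the window for a different reason.

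Section 3.0 hypothesises that the cream is safe and well tolerated. A non-significant count test could be read as supporting that hypothesis when it says little about tolerability.

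**Working it through.** **The plan's own figure.** No power or precision is stated for the safety endpoint. The stated figure is for ulcer response, 88% versus 48% with 20 completers per arm. Normal approximation with pooled null variance:
- SE0 = √(2 × 0.68 × 0.32 / 20) = 0.1475
- SE1 = √(0.88 × 0.12 / 20 + 0.48 × 0.52 / 20) = 0.1333
- power = Φ[(0.40 − 1.96 × 0.1475) / 0.1333] = 79.7%

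The exact power of the uncorrected chi-square test is 82.1%, so the stated figure of over 80% is reproduced, and 40 / (1 − 0.20) = 50 randomized. Neither bears on tolerability.

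**Inputs for the check.** From the documents: 50 randomized 1:1, so 25 per arm, and events counted only on treatment. Assumed, because the documents give no figures: Poisson background events with mean λ = 1, 2 or 4 per subject over full treatment; a toxicity stop adds one event and occurs at a uniformly distributed time; stop rates of 20%, 30% or 40% on active and 4% on placebo.

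**Weighting.** Suppose 10 of 25 active subjects have one treatment-ending toxicity each, 10 of 25 placebo subjects have one mild event each, and all others have none. The counts are identical and the Mann-Whitney p-value is 1.0.

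**Direction.** With stop probability p, the expected count per subject is λ(1 − p) + p(λ/2 + 1) = λ + p(1 − λ/2). The expected difference between arms is therefore (pA − pP)(1 − λ/2). For 40% versus 4%:
- λ = 1: 0.36 × 0.5 = +0.18 (1.20 versus 1.02)
- λ = 2: 0.36 × 0 = 0 (2.00 versus 2.00)
- λ = 4: 0.36 × (−1) = −0.36 (3.60 versus 3.96)

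Under these assumptions, more than two background events per subject makes the less tolerated arm look better on the mean count.

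**Rejection rates** (4,000 simulated trials per cell, two-sided 0.05):

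| λ | Stops, active vs placebo | Mean count, active vs placebo | Mann-Whitney rejects |
|---|---|---|---|
| 1 | 20% vs 4% | 1.11 vs 1.02 | 5.8% |
| 1 | 30% vs 4% | 1.15 vs 1.02 | 8.7% |
| 1 | 40% vs 4% | 1.20 vs 1.02 | 11.0% |
| 2 | 40% vs 4% | 1.99 vs 2.00 | 5.0% |
| 4 | 20% vs 4% | 3.80 vs 3.96 | 5.8% |
| 4 | 40% vs 4% | 3.60 vs 3.96 | 9.8% |

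**What a by-arm proportion can show.** The two-sided Fisher p-value for k of 25 versus 0 of 25 is 2 × C(25,k) / C(50,k):
- k = 3: 2 × 2,300 / 19,600 = 0.23
- k = 4: 2 × 12,650 / 230,300 = 0.11
- k = 5: 2 × 53,130 / 2,118,760 = 0.0502
- k = 6: 2 × 177,100 / 15,890,700 = 0.022

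Significance therefore needs at least six against none. Section 7.2 calls for stopping the study at three. At a true active rate of 20%, three or more of 25 occur with probability 90%; at 30%, 99%. Exact (Clopper-Pearson) 95% intervals remain informative: 0/25 gives 0 to 13.7%, and 3/25 gives 2.5% to 31%. If the rule is met before full enrolment, the denominators are smaller and the intervals wider.

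**The case against.** A reader might infer that the planned analysis cannot see intolerance at all. The documents do not support that. The frequency table would list stinging, hypotension and methemoglobinemia by name, since Table 2 of Section 12 treats them as adverse events. Pain at the wound is compared by arm in 8.1.3, Section 5.2 intends a blood pressure comparison with placebo, and a DSMB reviews all adverse events. What stands is narrower: the plan does not compare these toxicities by arm, grade them, or link them to stopping. The stopping rules and the DSMB protect subjects but do not estimate tolerability against placebo.

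A reader might also infer a large gain in power from testing discontinuations: at 20% versus 0% a Fisher test rejects in about 36-42% of simulated trials, and at 30% versus 0% in about 78-81%. This does not hold as a benefit for this trial. Those rates have no source in the documents, and zero on placebo is the most favourable case. With 4% on placebo the figures fall to about 23% and 60-62%. Above all, the three-discontinuation rule, applied as written, would usually halt the study before six against none could accrue.

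The count test can also do better than the table above suggests. Phase 1 recorded 16 diastolic pressure events in 4 participants, so an intolerant subject may log several events. If each logs three, with no truncation, Mann-Whitney power is about 13-22% at 20% stops and 25-44% at 30%. With a sparse background of 0.2-0.5 events per subject it is about 15-25% and 25-49%. The size of the insensitivity therefore depends on unknown rates. The equal weighting and the truncated window do not.

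**Conclusion.** The point holds as a gap between endpoint and analysis. Tolerability versus placebo is part of the primary endpoint and of the first aim, but no analysis is assigned to it. The one between-arm safety test is insensitive to treatment-ending toxicity and can favour the less tolerated arm.

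The equal weighting and the treatment-time window come directly from Sections 8.1.1 and 12. The numerical size rests on assumed stop rates, background rates and stopping times. Within the ranges tabulated, the test rejects in about 5-11% of trials, little above its 5% level, and the sign of the mean difference reverses once background events exceed two per subject. The case for change does not rest on a power advantage. It rests on having a defined tolerability estimate with an interval, in line with the emphasis on estimation in the sample-size rationale of Section 5.2. The change should be made, but its absence does not invalidate the trial.

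**What to change.** In Section 8.1.1, add a tolerability component to the primary endpoint: the proportion of randomized subjects in each arm with a dose-limiting toxicity or permanent cream discontinuation for toxicity. Report the between-arm difference with an exact 95% CI. A Fisher test may be reported as secondary. State in the text that the three-discontinuation rule limits what such a test can show.

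Keep the adverse-event count as the adverse-effect component, and also report events per unit of treatment time by arm, so that early stopping for toxicity or healing does not pass for fewer events.

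Before the component is coded, two things are needed:
- Sections 5.4 and 7.2 must be reconciled. They differ on methemoglobin (above 7% versus above 7.5%) and on the wording of hypotension. Which criterion applies is for the sponsor and investigators to settle.
- The reason for discontinuation should be recorded explicitly. Section 12 covers severity, relationship and management, but no such field is described.

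The cost is SAP wording, one reconciliation and possibly one case report form field, settled before unblinding. No visits or subjects are added. The small downside is one more safety comparison.
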